## 9.2. General Considerations

The test for non-inferiority between test product versus water in the examiner rating of dryness and redness will be one-sided at the 0.05 level of significance. All other statistical tests will be done at a two-sided 0.05 level of significance.

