### 9.3.2. Primary Analysis(es)

The primary endpoint will be tested for non-inferiority of the test product to water in change from baseline on Day 5 in examiner rating of dryness, using treatment estimates derived from an ANCOVA with subject (random effect), treatment and site as factors with baseline value as a covariate. The LSMeans will be presented for each treatment. The treatment difference (test product to water) and upper one-sided 95% confidence limit will be presented. If this upper confidence limit is below 0.25, it will be concluded that the test product is not inferior to water in the examiner rating of dryness.

This will be corroborated by using a one-sided 0.05 level of significance Wilcoxon sign rank test performed on the adjusted difference (within subject change from Baseline subtracted by 0.25) on Day 5 to test the hypothesis that the mean change from baseline for the test product is not greater than the change for water by 0.25 or more. The interpretation of this analysis will be assessed with caution as the non-

Document Name	GSK2017010007013		
Type	Version	Document Identifier	Effective Date
elido_clinicalelbc	1.0; CURRENT; Most-Recent; Effective	090032d580d0a8784	06-Mar-2018 06:52:18
Reason For Issue	Auto Issue		

inferiority margin of 0.25 is based on mean dryness score with assumption of normal rather than discreet distribution.

For individual subjects an increase in dryness score from baseline of 1 or more with treatment is considered as a clinically relevant irritation response, so additional analysis will be performed based on subjects with this response, with more details provided in the SAP.

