### 9.3.3. Secondary Analysis(es)

The non-inferiority analyses performed for primary endpoint will also be performed for the secondary endpoint based on examiner rating of redness on Day 5.

For secondary endpoints based on examiner rating of dryness and redness on Day 5 to compare positive control versus water, the same ANCOVA model as above will be used and the treatment difference (positive control to water), p-value and 95% confidence interval will be presented. Also for information, the treatment difference (positive control to test product) and treatment difference (water to unwashed), p-value, and 95% confidence interval will be presented.

For the other secondary endpoints of redness and dryness each day, TEWL and corneometer, the change from baseline will be analysed using ANCOVA with subject (random effect), treatment and site as factors with baseline value as a covariate. LSMeans for each treatment will be presented. The treatment differences (test product to water and positive control to water), p-value and 95% confidence intervals will be presented. Also for information, the treatment difference (positive control to test product) and treatment difference (water to unwashed), p-value, and 95% confidence interval will be presented.

If data are sufficiently non-normal in distribution, the non-parametric Wilcoxon signed ranks test will be used with median differences and 95% confidence interval presented based on the Hodges-Lehmann method.

Redness and dryness scores, TEWL and corneometer measurements at each time point and change from baseline in these scores and measurements at each time point will also summarized for test product, water, positive control and unwashed site using descriptive statistics such as the number of non-missing observations, mean, standard deviation, median, minimum, and maximum.

Document Name	GSK20170101Protocol001		
Type	Version	Document Identifier	Effective Date
elido_clinicalelbc	1.0; CURRENT; Most-Recent; Effective	090032d580d0a8784	06-Mar-2018 07:52:18
Reason For Issue	Auto Issue		

No adjustment will be made for multiplicity testing for the secondary endpoints, however consistency of effects will be taken into consideration in interpreting the results.

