| Minimum | —** | | —** | | —** | | —** | | |
| Maximum | —** | | —** | | —** | | —** | | |

Page x of y

PPD

Programming Note:

- Repeat for Day 5
- Also, for the corneometer assessment

| | | | |
|------------------|--|---------------------|----------------------|
| Document Name | gsk-207619-reporting-and-analysis-plan.pdf | | |
| Type | Version | Document Identifier | Effective Date |
| eldo_controlled | 1.0; CURRENT; Most-Recent; Effective | 090032d580e0a875 | 06-Apr-2018 06:53:51 |
| Reason For Issue | Auto Issue | | |

Protocol: 207619

Program Run Date:ddmonyyyy

Table 14.2.2.1
Statistical Analysis of Examiner Assessment of Dryness on Day 5, 3 Hour Post Last Wash Procedure
Intent to Treat Population

Intent to Treat Population N=XX)

| | Micellar cleanser | | Baxter Sterile Water | |
|---|-------------------|------------------------|----------------------|--------------|
| | (N = xx) | | (N = xx) | |
| | Baseline [1] | Change | Baseline [1] | Change |
| Day 5, 3 hour post last wash | | | | |
| n | xx | xx | xx | xx |
| Missing | xx | xx | xx | xx |
| Mean | xx.x | xx.x | xx.x | xx.x |
| SD | xx.xx | xx.xx | xx.xx | xx.xx |
| SE | xx.xx | xx.xx | xx.xx | xx.xx |
| Median | xx.x | xx.x | xx.x | xx.x |
| Minimum | xx | xx | xx | xx |
| Maximum | xx | xx | xx | xx |
| Adjusted Mean (SE) [2] | | xx.x (xx.xx) | | xx.x (xx.xx) |
| 90% CI [2] | | (xx.x, xx.x) | | (xx.x, xx.x) |
| P-value [2] | | 0.xxxx | | 0.xxxx |
| Comparison Between Treatments | Difference [2,3] | Upper One-sided 90% CI | P-value | |
| Micellar cleanser vs Baxter Sterile Water | xx.x | (xx.x, xx.x) | 0.xxxx | |

[1] Baseline visit is day 1(AM) visit 2 assessment. Baseline only includes those subjects who have a corresponding post-baseline assessment.

[2] From ANOVA model with change from baseline in examiner assessment on dryness as response and treatment, site as fixed effects. If one-sided upper 95% CI is less than 0.25 then non-inferiority is established.

[3] Difference is first named treatment minus second named treatment such that a negative difference favours first named treatment.

[4] P-value from Wilcoxon sign rank test, which is based on the adjusted differences. Adjusted difference is calculated in the following manner;

Page x of y

PPD

Protocol: 207619

Program Run Date:ddmonyyyy

| | | | | | | | | | | | | |
|------------------|--|--|--|--|--|--|--|--|--|--|--|--|
| Document Name | gsk-207619-reporting-and-analysis-plan.pdf | | | | | | | | | | | |

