| Adjusted Mean (SE) [2] | | xx.x (xx.xx) | | xx.x (xx.xx) | | xx.x (xx.xx) | | xx.x (xx.xx) |
| 95% CI [2] | | (xx.x, xx.x) | | (xx.x, xx.x) | | (xx.x, xx.x) | | (xx.x, xx.x) |
| P-value [2] | | 0.xxxx | | 0.xxxx | | 0.xxxx | | 0.xxxx |
| Comparison Between Treatments | Difference [2,3] | | 95% CI | | P-value | | | |
| Micellar cleanser vs Baxter Sterile Water | xx.x | | (xx.x, xx.x) | | 0.xxxx | | | |
| Imperial leather Original bar Soap vs. Baxter Sterile Water | | | | | | | | |
| Imperial leather Original bar Soap vs. Micellar cleanser | | | | | | | | |
| Baxter Sterile Water vs.Un-washed | | | | | | | | |

| | | | |
|------------------|--|---------------------|----------------------|
| Document Name | gsk-207619-reporting-and-analysis-plan.pdf | | |
| Type | Version | Document Identifier | Effective Date |
| eldo_controlled | 1.0; CURRENT; Most-Recent; Effective | 090032d580e0a875 | 06-Apr-2018 06:53:51 |
| Reason For Issue | Auto Issue | | |

Supportive Non-Parametric Analysis

(xx.x, xx.x)

0.xxxx

[4]

[1] Baseline visit is day 1(AM) visit 2 assessment. Baseline only includes those subjects who have a corresponding post-baseline assessment.

[2] From ANOVA model with change from baseline in examiner assessment on dryness as response and treatment, site as fixed effects. If one-sided upper 95% CI is less than 0.25 then non-inferiority is established.

[3] Difference is first named treatment minus second named treatment such that a negative difference favours first named treatment.

[4] P-value from Wilcoxon sign rank test, 95% CI is constructed on the Hodges-Lehmann method.

Page x of y

PPD

██████████

Programming Note:

- Repeat for day 3, 4 and 5, 3 hour post last wash
- Non-parametric method will be presented only if there is violation of normality.
- For the Table 14.2.2.4 the footnotes will be modified as following -

[1] Baseline visit is day 1(AM) visit 2 assessment. Baseline only includes those subjects who have a corresponding post-baseline assessment.

[2] From ANOVA model with change from baseline in examiner assessment on redness as response and treatment, site as fixed effects.

[3] Difference is first named treatment minus second named treatment such that a negative difference favours first named treatment.

[4] P-value from Wilcoxon sign rank test, 95% CI is constructed on the Hodges-Lehmann method.

- For the Table 14.2.2.5 and 6 the footnotes will be modified as following -

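### The daily-dryness table shell attaches an unplanned non-inferiority declaration to Days 2 to 4, and the SAP's 90% limit leaves the planned Day 5 rule inconsistent

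*SAP*

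**What the plan says.** Table numbers here follow the table list and shells of the amended SAP. Its Section 2.5.1 still cites the daily tables under older numbers.

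- **Protocol 9.2** sets the error rates: "The test for non-inferiority between test product versus water in the examiner rating of dryness and redness will be one-sided at the 0.05 level", and "All other statistical tests will be done at a two-sided 0.05 level of significance". The first sentence names no day. The analysis sections do.
- **Protocol 9.3.2** (Day 5 dryness, primary): "The treatment difference (test product to water) and upper one-sided 95% confidence limit will be presented". Then: "If this upper confidence limit is below 0.25, it will be concluded that the test product is not inferior to water".
- **Protocol 9.3.3** extends this to one further endpoint: "The non-inferiority analyses performed for primary endpoint will also be performed for the secondary endpoint based on examiner rating of redness on Day 5". Dryness and redness on each day get differences, p-values and 95% confidence intervals, with no margin.
- **SAP 2.5.1** gives the daily scores adjusted means, 95% intervals and p-values. It states no non-inferiority rule for them and does not list test product versus water among the daily comparisons.
- **SAP 2.4.1.2** concludes Day 5 dryness non-inferiority from an upper one-sided 90% limit below 0.25.
- **SAP 5.1, Table 14.2.2.1 shell** (Day 5 dryness) has the column "Upper One-sided 90% CI", but its footnote [2] says "If one-sided upper 95% CI is less than 0.25 then non-inferiority is established".
- **SAP 5.1, Table 14.2.2.3 shell** (daily dryness) carries the same sentence in its footnote [2], with the programming note "Repeat for day 3, 4 and 5, 3 hour post last wash". The substitute footnote for daily redness (Table 14.2.2.4) has the same model wording without that sentence.

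**The concern.** A table footnote that says when non-inferiority is established is a decision rule. Read literally, this one allows a conclusion on Days 2, 3 and 4, for which the protocol sets no margin and SAP 2.5.1 no rule. Those days are scored after fewer washes than Day 5, so a pass may be easier to obtain. A report programmed from the shell could print up to three statements that the cleanser is no more drying than water without any having been planned. SAP Section 3, which lists changes from the protocol, does not mention them.

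A separate matter meets this one on Day 5. The daily table repeats the primary contrast from the same model, and its footnote uses one-sided 95%, while SAP 2.4.1.2 uses one-sided 90%. Two outputs could then support opposite conclusions on the primary endpoint.

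**Working it through.** **1. Which days are planned.**

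| Dryness, test product minus water | Protocol 9.3.2-9.3.3 | SAP text | Table 14.2.2.3 footnote [2] |
|---|---|---|---|
| Days 2, 3, 4 | difference, p-value, 95% CI | no non-inferiority rule (2.5.1) | non-inferiority if one-sided 95% limit < 0.25 |
| Day 5 | non-inferiority, one-sided 95% limit < 0.25 | non-inferiority, one-sided 90% limit < 0.25 (2.4.1.2) | non-inferiority if one-sided 95% limit < 0.25 |

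The footnote departs from the protocol on Days 2 to 4 only. On Day 5 it agrees with the protocol, and the SAP text does not.

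**2. Exposure at scoring.** There are four washes per site on Days 1 to 4 and two on Day 5, and scoring on Days 2 to 4 precedes the PM washes. Washes before scoring are 4 + 2 = 6 (Day 2), 8 + 2 = 10 (Day 3), 12 + 2 = 14 (Day 4) and 16 + 2 = 18 (Day 5).

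**3. Day 5 thresholds.** Inputs are SD of the within-subject difference 0.25 (Protocol 9.1, SAP 2.8), n = 40 completers (same sections) and margin 0.25. The plan's sample size cannot be reproduced because the rest of the calculation is redacted.

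SE = 0.25/√40 = 0.0395. The largest passing difference is 0.25 − t × SE, with 39 degrees of freedom:

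- one-sided 90%: 0.25 − 1.304 × 0.0395 = 0.198
- one-sided 95%: 0.25 − 1.685 × 0.0395 = 0.183
- upper end of a two-sided 95% interval: 0.25 − 2.023 × 0.0395 = 0.170

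Observed differences between about 0.183 and 0.198 therefore pass at 90% and fail at 95%. At a true difference of 0.25 the two rules disagree in 0.10 − 0.05 = 5% of trials. With the ANOVA's 114 degrees of freedom the first two limits are 0.199 and 0.184.

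The third line matters because Table 14.2.2.3 displays only a 95% CI. If that is two-sided, as Protocol 9.2 implies, the limit named in the footnote is not shown.

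**4. Days 2 to 4, if a pass on any one day were claimed.** Assume a true excess of exactly 0.25 on each of the three days, each tested at one-sided 0.05.

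- Independent days: 1 − 0.95³ = 0.143.
- Assumed equal between-day correlation, simulated (40,000 trials, n = 40, SD 0.25): 0.118 at 0.5, 0.103 at 0.7 and 0.079 at 0.9.

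**The case against.** The strongest reply is that this is leftover shell text, not an analysis plan. The sentence names no day, and the table includes Day 5, where the rule is valid. The daily redness footnote omits it, and the limit it needs is not displayed. The amended Table 14.2.2.1 also keeps an orphan Wilcoxon footnote, so carry-over is evident elsewhere. SAP 2.4.1.2 ties the primary conclusion to Table 14.2.2.1, and secondary endpoints are openly unadjusted for multiplicity. Most of this stands and is why the point is minor. It does not clear the footnote, which as written applies to every day the shell is repeated for.

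A reader might infer three stronger things:

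- *That Day 5 non-inferiority in this table is also unplanned.* It is the protocol's primary analysis, with this same limit and margin.
- *That the footnote introduces a new rule for Day 5.* Table 14.2.2.1 footnote [2] carries the identical sentence. The outlier is the 90% limit in SAP 2.4.1.2 and in that table's column, a conflict that would exist without Table 14.2.2.3.
- *That the trial's false-positive rate rises to 1 − 0.95⁴ = 18.5%.* That counts the planned Day 5 test and needs success defined as a pass on any day, which neither document says. It also needs an excess of 0.25 on every day, which sits badly with lower early exposure: if the early excess is below 0.25, an early non-inferiority statement is true.

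The 90% limit may have been meant as the upper end of a two-sided 90% interval, which is the one-sided 95% limit; the shell prints a pair of limits. The SAP text says one-sided, however, and as written it is alpha 0.10.

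**Conclusion.** The point holds for Days 2 to 4: the footnote states a non-inferiority rule that neither Protocol 9.3.2-9.3.3 nor SAP 2.5.1 plans, and the parallel redness footnote lacks it. Carry-over from Table 14.2.2.1 is the likely explanation, though the documents do not say so. The primary Day 5 alpha is not affected by Days 2 to 4. The 14.3% figure, and the roughly 12% to 8% under correlation, apply only if a single early pass is claimed and the true excess is 0.25 on all three days; the correlations are assumptions.

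The Day 5 inconsistency is real but comes from the SAP's 90% limit. The band of about 0.183 to 0.198 rests on the planning SD of 0.25 and 40 completers. Severity is minor.

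**What to change.** 1. Delete the non-inferiority sentence from footnote [2] of Table 14.2.2.3, as in the daily redness footnote.
2. State in the SAP that dryness non-inferiority is concluded only from Table 14.2.2.1 at Day 5, using the protocol's one-sided 95% upper limit (alpha 0.05).
3. Change SAP 2.4.1.2 and the Table 14.2.2.1 column from 90% to match. Day 5 redness uses the same shell and its rule in SAP 2.5.1 has the same 90% limit, so align it in the same edit.

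The first step alone leaves the Day 5 conflict, and the third alone leaves the declarations on Days 2 to 4.

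The cost is text and shell edits, plus a slightly stricter Day 5 limit than the SAP text now states. At SD 0.25 and n = 40 the chance of passing goes from 99.3% to 98.1% at a true difference of 0.10, and from 88.9% to 80.0% at 0.15. At a true difference of zero it stays at essentially 100%.

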## 5.3. Product Assignment

Each subject will have the test product, positive control (Imperial Leather Original bar soap), negative control (sterile water) and an unwashed site randomly assigned to sites on each volar forearm. The specific site locations will be assigned to subjects in

Document Name	GSK2017010007013		
Type	Version	Document Identifier	Effective Date
elido_clinicalelbc	1.0; CURRENT; Most-Recent; Effective	090032d580d0a8784	06-Mar-2018 07:52:18
Reason For Issue	Auto Issue		

accordance with the randomisation schedule generated prior to the start of the study, using validated software.

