#### 9.3.4. Safety Analysis(es)

Adverse Events (AE) will be tabulated according to the current version of the Medical Dictionary for Regulatory Activities (MedDRA). Frequencies and percentages will be presented overall, for each system organ class, and for each preferred term. Summaries of treatment-emergent AE's, treatment-related AE's, and AE's leading to discontinuation, and serious AE's will be completed. For treatment-related AE's, these will also be presented by treatment/test site.

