2.5.2 Safety

2.5.2.1 Adverse events and Serious Adverse Events

All adverse events (AEs) will be listed in the ([Listing 16.2.7.1](#)) for the randomised subjects and all adverse events for the non-randomised subjects will be listed in [Listing 16.2.7.2](#).

| | | | |
|------------------|--|---------------------|----------------------|
| Document Name | gsk-207619-reporting-and-analysis-plan.pdf | | |
| Type | Version | Document Identifier | Effective Date |
| eldo_controlled | 1.0; CURRENT; Most-Recent; Effective | 090032d580e0a875 | 06-Apr-2018 06:53:51 |
| Reason For Issue | Auto Issue | | |

Treatment emergent adverse events (TEAEs) will be summarized by the number and percentage of subjects having any adverse event, an adverse event in each System Organ Class, and each individual adverse event ([Table 14.3.1.1](#)). All TEAEs will also be tabulated by severity and treatment ([Table 14.3.1.2](#)). Treatment-emergent AEs suspected of a relationship to study medication and those causing study discontinuation will be presented in a similar manner ([Table 14.3.1.3](#)). For treatment-related AEs, these will also be presented by severity and treatment, if applicable ([Table 14.3.1.4](#)).

Non-fatal serious adverse events and adverse events causing study treatment discontinuation will be listed ([Listing 14.3.2.1](#)).

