5.1 Templates for the Tables, listings and figures

This is a guideline which will give the guidance of treatment labels that will be used for the table header and in the figures, listings and in the footnotes.

The treatment labels for the column heading will be as follow:

- Micellar cleanser
- Imperial Leather Original Bar Soap
- Baxter Sterile Water
- Unwashed

| | | | |
|------------------|--|---------------------|----------------------|
| Document Name | gsk-207619-reporting-and-analysis-plan.pdf | | |
| Type | Version | Document Identifier | Effective Date |
| eldo_controlled | 1.0; CURRENT; Most-Recent; Effective | 090032d580e0a875 | 06-Apr-2018 06:53:51 |
| Reason For Issue | Auto Issue | | |

Protocol: 207619

Program Run Date:ddmonyyyy

Table 14.1.1
Subject Disposition
All Screened Subjects

All Screened Subjects (N=XX)

| | Overall(N=XX) |
|-----------------------------------|---------------|
| | n (%) |
| TOTAL NUMBER OF SUBJECTS SCREENED | xx (xx.x) |
| SUBJECTS NOT RANDOMISED | xx (xx.x) |
| DID NOT MEET STUDY CRITERIA | xx (xx.x) |
| ADVERSE EVENTS | xx (xx.x) |
| ETC. | xx (xx.x) |
| SUBJECTS RANDOMISED | xx (xx.x) |
| COMPLETED | xx (xx.x) |
| DID NOT COMPLETE | xx (xx.x) |
| ADVERSE EVENT | xx (xx.x) |
| LOST TO FOLLOW UP | xx (xx.x) |
| PROTOCOL DEVIATION | xx (xx.x) |
| WITHDRAWAL OF CONSENT | xx (xx.x) |
| OTHER | xx (xx.x) |
| RANDOMISED POPULATION | xx (xx.x) |
| SAFETY POPULATION | xx (xx.x) |
| INTENT TO TREAT POPULATION | xx (xx.x) |

Page x of y

| | | | |
|------------------|--|---------------------|----------------------|
| Document Name | gsk-207619-reporting-and-analysis-plan.pdf | | |
| Type | Version | Document Identifier | Effective Date |
| eldo_controlled | 1.0; CURRENT; Most-Recent; Effective | 090032d580e0a875 | 06-Apr-2018 06:53:51 |
| Reason For Issue | Auto Issue | | |

Protocol: 207619

Program Run Date:ddmonyyyy

Table 14.1.4.1
Subject Demographics and Baseline Characteristics
Safety Population

Safety Population (N=XX)

| Demographic variables | Overall (N=XX) |
|---|-------------------|
| SEX n (%) | |
| MALE | xx (xx.x) |
| FEMALE | xx (xx.x) |
| RACE n (%) | |
| ASIAN | |
| BLACK OR AFRICAN AMERICAN | |
| AMERICAN INDIAN OR ALASKA NATIVE | xx (xx.x) |
| NATIVE HAWAIIAN OR OTHER PACIFIC ISLANDER | xx (xx.x) |
| WHITE | xx (xx.x) |
| MULTIPLE | xx (xx.x) |
| AGE (YEARS) | |
| N | XX |
| MEAN | XX.X |
| SD | XX.XX |
| MEDIAN | XX.X |
| MINIMUM | XX |
| MAXIMUM | XX |
| FITZPATRICK SCALE FOR SKIN TYPE | |

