- [1] Baseline visit is day 1 visit 2 assessment. Baseline only includes those subjects who have a corresponding post-baseline assessment.
- [2] From ANCOVA model with change from baseline in examiner assessment on redness as response and treatment, site as fixed effects and examiner assessment on TEWL/Corneometer as covariates.
- [3] Difference is first named treatment minus second named treatment such that a negative difference favours first named treatment.
- [4] P-value from Wilcoxon sign rank test, 95% CI is constructed on the Hodges-Lehmann method.

| | | | |
|------------------|--|---------------------|----------------------|
| Document Name | gsk-207619-reporting-and-analysis-plan.pdf | | |
| Type | Version | Document Identifier | Effective Date |
| eldo_controlled | 1.0; CURRENT; Most-Recent; Effective | 090032d580e0a875 | 06-Apr-2018 06:53:51 |
| Reason For Issue | Auto Issue | | |

Protocol: 207619

Program Run Date: ddmonyyyy

Table 14.3.1.1
Summary of Treatment Emergent Adverse Event
Safety Population

Safety Population: N=xx

| System Organ Class Preferred Term | Micellar cleanser (N = xx) | Imperial Leather Original Bar | | Baxter Sterile Water (N = xx) | | Unwashed (N=xx) | |
|---|-------------------------------|-------------------------------|------------------|----------------------------------|-----------|--------------------|-----------|
| | n (%) | nAE | Soap (N = xx) | nAE | n (%) | nAE | n (%) |
| NUMBER OF SUBJECTS WITH AT LEAST ONE AE | xx (xx.x) | xx | xx (xx.x) | xx | xx (xx.x) | xx | xx (xx.x) |
| NUMBER OF SUBJECTS WITH NO AE | xx (xx.x) | xx | xx (xx.x) | xx | xx (xx.x) | xx | xx (xx.x) |
| SKIN RELATED AES | xx (xx.x) | xx | xx (xx.x) | xx | xx (xx.x) | xx | xx (xx.x) |
| SKIN AND SUBCUTANEOUS TISSUE DISORDERS | xx (xx.x) | xx | xx (xx.x) | xx | xx (xx.x) | xx | xx (xx.x) |
| ERYTHEMA | xx (xx.x) | xx | xx (xx.x) | xx | xx (xx.x) | xx | xx (xx.x) |
| DERMATITIS | xx (xx.x) | xx | xx (xx.x) | xx | xx (xx.x) | xx | xx (xx.x) |
| NON SKIN RELATED AES | xx (xx.x) | xx | xx (xx.x) | xx | xx (xx.x) | xx | xx (xx.x) |
| GASTROINTESTINAL SYSTEM | xx (xx.x) | xx | xx (xx.x) | xx | xx (xx.x) | xx | xx (xx.x) |
| ABDOMINAL PAIN | xx (xx.x) | xx | xx (xx.x) | xx | xx (xx.x) | xx | xx (xx.x) |
| DRY MOUTH | xx (xx.x) | xx | xx (xx.x) | xx | xx (xx.x) | xx | xx (xx.x) |
| VOMITTING | xx (xx.x) | xx | xx (xx.x) | xx | xx (xx.x) | xx | xx (xx.x) |

n (%) = Number (percent) of subjects nAE = Number of adverse events.

Page x of y

PPD

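### The adverse-event tables have four site columns and no overall column, so overall subject incidence cannot be read from them and events with no test site have no stated place

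*SAP*

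**What the plan says.** **Design.** Protocol 5.3 gives each subject the test product, the positive control, and a "negative control (sterile water) and an unwashed site randomly assigned to sites on each volar forearm". The conditions run concurrently within a person, not in separate groups.

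**Protocol safety plan.** For adverse events, section 9.3.4 says: "Frequencies and percentages will be presented overall, for each system organ class, and for each preferred term". It then adds: "For treatment-related AE's, these will also be presented by treatment/test site".

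**SAP text.** Section 2.5.2.1 describes Table 14.3.1.1 as counts and percentages of subjects with any event, by system organ class and by individual event. It mentions no treatment split. For Table 14.3.1.2 it says: "All TEAEs will also be tabulated by severity and treatment".

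**SAP shells.** Section 5.1 introduces the column labels with "The treatment labels for the column heading will be as follow" and then lists only the four conditions. The amended shells for Tables 14.3.1.1 and 14.3.1.2 follow that list. Both include a "NON SKIN RELATED AES" block with example rows such as "ABDOMINAL PAIN" under the condition columns, Unwashed among them. The footnote defines the cells: "n (%) = Number (percent) of subjects nAE = Number of adverse events". The table list in section 4.2 reuses these two templates for Tables 14.3.1.3 and 14.3.1.4. The pre-amendment shells have the same layout, so an Overall column is unlikely to have been lost when the PDF was read. The disposition and demographics shells do use an Overall column.

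**The concern.** In a parallel-group trial, one column per treatment gives each subject one place, and the columns can be added. Here the same people stand behind all four columns. This causes two problems.

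1. A subject may have events at one site or at several. The four column counts therefore do not determine how many distinct subjects had any event, which is the overall figure that the protocol promises.
2. An event such as abdominal pain does not belong to a 3x3 cm patch of forearm. The shells still provide cells for it under each condition, and no SAP text, footnote or programming note says how to fill them.

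Non-local events are to be expected. Protocol 7.2 collects events from first use of the washout soap until 5 days after the last product administration, and 7.4 has subjects asked at each visit whether they felt unwell. General safety of the test product is a stated secondary objective, so the summary tables need to answer that question.

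**Working it through.** The documents give no adverse-event figure, so there is none to reproduce. The check compares the texts with the shells and then counts.

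**Step 1. Texts against shells**

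| Source | Overall presentation | Split by condition |
|---|---|---|
| Protocol 9.3.4 | Yes: overall, by class and by term | Added for treatment-related events |
| SAP 2.5.2.1, Table 14.3.1.1 | Implied: no treatment split mentioned | None mentioned |
| SAP 2.5.2.1, Table 14.3.1.2 | Not mentioned | All treatment-emergent events, by severity and treatment |
| Shells 14.3.1.1 and 14.3.1.2 (and 14.3.1.3, 14.3.1.4 by reuse) | No column | All events, including non-skin |

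The shell for Table 14.3.1.1 therefore differs from both its own SAP text and the protocol. SAP section 3, which records changes from the protocol, mentions only the removal of the Wilcoxon-type test.

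**Step 2. Can the overall count be recovered from the four columns?**

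Inputs: N = 45, the planned number randomised (Protocol 9.1, SAP 2.8), and column counts a₁ to a₄ of subjects with at least one event. The counts below are assumed for illustration.

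The number of distinct subjects D satisfies max(aᵢ) ≤ D ≤ min(N, Σaᵢ). The lower limit applies when the subjects in the smaller columns all appear in the largest one. The upper limit applies when no subject appears twice.

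With counts of 3, 6, 2 and 1:
- lower limit: max = 6, and 6/45 = 13.3%
- upper limit: 3 + 6 + 2 + 1 = 12, and 12/45 = 26.7%

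The same four columns fit any overall count from 6 to 12. This holds for purely local skin events too, so it does not depend on where site-less events are placed.

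**Step 3. What happens to an event with no test site?**

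Assume k such events, each in a different subject, with k from 1 to 5 and no other events. The true incidence is k/45, which is 1/45 = 2.2% for k = 1 and 5/45 = 11.1% for k = 5.

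| Way of filling the columns | Each column shows | Consequence |
|---|---|---|
| Repeated in all four | 2.2% to 11.1% in every column | Correct incidence in that row, but shown as if tied to each site; event counts across columns sum to 4k (4 to 20) |
| Assigned to one | 2.2% to 11.1% in one column, 0% in the other three | False contrast between products |
| Left out | 0% in all four | Events missing; subjects with no event overstated by k (1 to 5) in each column |

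The SAP permits all three readings and chooses none.

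**The case against.** The strongest reply is that little is actually wrong. The SAP sentence for Table 14.3.1.1 has no treatment split and agrees with the protocol. The sentence about severity and treatment belongs to Table 14.3.1.2 and is worded as an addition. On this view the plan is sound and only a mock shell is mis-drawn. The non-skin rows are placeholders, the study lasts five days in about 45 healthy people, and every event is listed by subject number, so distinct-subject counts can be rebuilt by hand.

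Much of this is right, and it limits the point. A reader might infer three stronger things that the documents do not support:

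- **That whole-body events will be counted four times.** No passage prescribes this. It is one of three ways to fill the shell. Even then each column shows the correct subject incidence, such as 5/45, and the inflated total of 20 appears only if someone adds the columns. The shell has no total.
- **That the per-product counts are necessarily wrong.** They mislead about products if a site-less event is assigned to one column. Under repetition they are redundant rather than false.
- **That the protocol restricts the by-site split to treatment-related events.** It says that those events will also be shown by site. It does not exclude a further split.

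What remains is that programmers work from the shells, and all four tables inherit a layout with no overall count and no placement rule. The listings lessen the harm but do not replace a summary table. Listing 16.2.7 is itself headed by treatment group, so it raises the same placement question.

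**Conclusion.** The point holds as a defect in the summary tables. As drawn, none of the four planned adverse-event tables gives the number of distinct subjects with any event, although the protocol promises an overall presentation. Events with no test site appear under product columns without a rule.

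The size depends on events not yet seen. In the illustration, overall incidence is uncertain between 13.3% and 26.7%. One to five site-less events placed in a single column would show 2.2% to 11.1% for one product against 0% for the rest. These figures assume 45 subjects and invented event counts. They show the mechanism and do not predict results.

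The missing column and the missing rule are clear from the documents; any actual miscounting is not, because it depends on a choice the SAP leaves open. No inferential result is affected, the primary endpoint included. The change should be made, but the trial's main conclusion does not turn on it.

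**What to change.** - Add an Overall column to Tables 14.3.1.1 to 14.3.1.4, with N equal to the Safety population and each subject counted once per row. Show every event in it.
- Use the four condition columns only for events located at a specific test site.
- Show events with no test site in the Overall column only. This includes non-skin events judged treatment-related, so that one rule covers all four tables.
- State the rule in SAP 2.5.2.1, revise its sentence for Table 14.3.1.2 to match, and apply the same rule to the treatment-group heading of Listing 16.2.7.

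The cost is a wording and shell edit, plus one check of the data. Listing 16.2.7 has a column named Site, but the SAP does not define it as the forearm test site. The sponsor should confirm that the adverse-event data record the test site before relying on that field.
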